4.1.5 Blinding and procedures for unblinding

4.1.5.1 Blinding

To maintain the treatment blind during the trial, all patients will receive the blinded treatments every 4 weeks. Please refer to [Section 4.1.4](#) and [Table 4.1.4: 1](#) for further details.

The sponsor will remain blinded with regard to the randomized treatment assignments until the last randomized patient has completed or early discontinued from the 48 week treatment period of the trial and the database is considered ready for unblinding to perform the primary analysis of the trial. Note that for the planned interim analysis of this trial (see details in [Section 7.2.7](#)), only clinical efficacy and safety data for the OL i.v. rescue treatment and OL s.c. maintenance treatment periods are intended to be reported; no unblinding of the initial randomized s.c. treatments is required..

With database lock for the primary trial analysis, the sponsor (including all trial personnel) will be officially unblinded to the randomization details; investigators and patients will remain blinded until the official end of the trial (final trial analysis) when the last patient has completed through 16 weeks of trial safety follow-up (if applicable).

If the trial team agrees to perform the primary analysis and final analysis as one single analysis (at the time of trial completion), then patients, investigators, and sponsor personnel involved in the trial conduct will be unblinded to the randomized treatment assignments after the database lock has been performed.

The randomization codes will be provided to bioanalytics prior to last patient out of the trial to allow for the exclusion from the analyses of PK samples taken from placebo patients. Bioanalytics will not disclose the randomization code or the results of individual measurements until the trial has been officially un-blinded to the sponsor. Sample drug levels and demographic data together with treatment assignments and dosing information may be made available to named individuals from the bioanalytics department for the purpose of PK dataset generation and analysis in accordance with the sponsor's standard procedures.

A fully external DMC will perform an unblinded safety and efficacy assessment at specified intervals in order to ensure that patients are protected from potential harm, please refer to [Section 8.7](#) for further details.

Section 4.1.5.2 provides the rules surrounding breaking of the randomization code.

4.1.5.2 Unblinding and breaking the code

Emergency unblinding will be available to the investigator / designee via IRT (for Japan: only to the investigator). It must only be used in an emergency situation when the identity of the trial drug must be known to the investigator in order to provide appropriate medical treatment or otherwise assure the safety of trial participants. The reason for unblinding must be documented in the source documents and/or appropriate eCRF page along with the date and the initials of the person who broke the code.

In case the automated unblinding option via the IRT system is malfunctioning, the IRT service provider can be contacted (24 hours a day coverage) and the treatment allocation can be obtained. IRT support has direct access to the database and the treatment information can be manually obtained in case the automated process is not working properly. Details about this process will be included in the ISF.

Due to the requirements to report Suspected Unexpected Serious Adverse Reactions (SUSARs), it may be necessary for a representative from BI's Pharmacovigilance group to access the randomisation code for individual patients during trial conduct. The access to the code will only be given to authorised Pharmacovigilance representatives for processing in the PV database system and not be shared further.

4.1.6 Packaging, labelling, and re-supply

The investigational medicinal products will be provided by Boehringer Ingelheim Pharma GmbH & Co. KG, Biberach, Germany. They will be packaged and labelled in accordance with the principles of Good Manufacturing Practice (GMP). Re-supply to the sites will be managed via an IRT system, which will also monitor expiry dates of supplies available at the sites.

For details of packaging and the description of the label, refer to the ISF.

4.1.7 Storage conditions

Drug supplies will be kept in their original packaging and in a secure limited access storage area according to the recommended storage conditions on the medication label. A temperature log must be maintained for documentation.

If the storage conditions are found to be outside the specified range, the CT Manager, as provided in the list of contacts, must be contacted immediately.

The trial medication must be administered in the manner specified in the CTP and instructions for IMP preparation handling and administration of BI 655130 or Placebo.

4.1.8 Drug accountability

The investigator or designee will receive the investigational drugs delivered by the sponsor when the following requirements are fulfilled:

- Approval of the clinical trial protocol by the IRB / ethics committee,
- Availability of a signed and dated clinical trial contract between the sponsor and the investigational site,
- Approval/notification of the regulatory authority, e.g. competent authority,
- Availability of the curriculum vitae of the Principal Investigator,
- Availability of a signed and dated clinical trial protocol,
- Availability of the proof of a medical license for the Principal Investigator,
- Availability of FDA Form 1572 (if applicable).

Investigational drugs are not allowed to be used outside the context of this protocol. They must not be forwarded to other investigators or clinics.

The investigator or designee must maintain records of the product's delivery to the trial site, the inventory at the site, the use by each patient, and the return to the sponsor or warehouse /

drug distribution centre or alternative disposal of unused products. If applicable, the sponsor or warehouse / drug distribution centre will maintain records of the disposal.

These records will include dates, quantities, batch / serial numbers, expiry ('use-by') dates, and the unique code numbers assigned to the investigational medicinal product and trial patients. The investigator or designee will maintain records that document adequately that the patients were provided the doses specified by the Clinical Trial Protocol (CTP) and reconcile all investigational medicinal products received from the sponsor. At the time of return to the sponsor, the investigator or designee must verify that all unused drug supplies have been returned by the clinical trial staff and all used or partially used supplies have been destroyed by the trial site, and that no remaining supplies are in the investigator's possession.

4.2 OTHER TREATMENTS, EMERGENCY PROCEDURES, RESTRICTIONS

4.2.1 Other treatments and emergency procedures

All concomitant medications should be carefully evaluated by the investigator and the Clinical Trial Manager (CTM) should be contacted when there are questions regarding concomitant medications.

The use of Investigator Prescribed SoC will lead to the discontinuation of the trial treatment except for the use of topical treatment/topical corticosteroids, methotrexate, cyclosporine and retinoids during OL rescue treatment period (4 weeks following i.v. dose rescue treatment with OL BI 655130 at R1/D1) and OL maintenance treatment period. Please refer to [section 4.2.2.2](#) and [section 3.1](#) for further details. Also, please refer to [section 3.3.4.1](#) for further details on handling of patients with premature treatment discontinuation.

The sponsor will not provide/supply SoC treatment (s) to the sites.

4.2.1.1 Emergency procedures

Systemic hypersensitivity including infusion reactions and anaphylactic reaction

In case of systemic hypersensitivity including infusion reactions and anaphylactic reaction, emerging during or after infusion/injection of study medication, the investigator should consider in accordance with severity of the reaction and local standard of care to

- Immediately interrupt the infusion/injection
- Treat with systemic anti-histamines, i.v. steroids, and in case of a severe allergic reaction (e.g., anaphylactic reaction) epinephrine

Also draw a plasma sample for IgE and ADA and a serum sample for neutralizing antibody (Nab) as detailed in the Lab Manual (Central Laboratory). Consider also the evaluation of histamine, serum tryptase, and complement components.

In case of systemic hypersensitivity including infusion reactions, based on patient's clinical course and medical judgment, the infusion may be re-initiated in case of mild or moderate systemic hypersensitivity including infusion reactions (according to RCTC grading [R13-3515] in ISF) at lower speed with gradual increase to complete the infusion as detailed in the *Instructions for Preparation and Handling of BI 655130* in the ISF. Regardless, the total duration of infusion should not exceed 180 minutes (3 hours).

In case of anaphylactic reactions based on published criteria ([Appendix 10.1.6](#); [R11-4890](#)) that are suspected to be caused by the study medication, the investigator should discontinue treatment with BI 655130.

When a non-acute hypersensitivity reaction related to immune complexes (i.e., serum sickness) is suspected, draw a sample for the laboratory assessment for circulating immune complexes.

In case of potential systemic allergic reaction, blood samples for determination of serum tryptase will be collected 0.5 h, 2 h, 6 h, 24 h after onset of the event.

Severe infections (according to RCTC grading: refer to the ISF), serious infections, opportunistic or mycobacterium tuberculosis infections

Treatment of the infection should be initiated promptly according to local standard of care. No further study medication should be administered until the active infection has resolved. Treatment with BI 655130 may be restarted when the patient has recovered according to investigator's assessment.

Malignancies

In case of occurrence of malignant neoplasm other than appropriately treated basal cell carcinoma or squamous cell carcinoma of the skin or in situ carcinoma of uterine cervix, treatment discontinuation is to be a consideration if deemed clinically appropriate by the investigator. In addition, diagnostics and treatment are to be initiated according to local standard of care.

4.2.1.2 Additional treatments

No additional treatment is planned.

However, in case of AEs in need of treatment, the investigator can authorize symptomatic therapy. In those cases, patients will be treated as necessary and, if required, kept under supervision at the trial site or transferred to a hospital until all medical evaluation results have returned to an acceptable level.

All concomitant and/or rescue therapies will be recorded on the appropriate pages of the electronic CRF (eCRF).

4.2.2 Restrictions

4.2.2.1 Restrictions regarding concomitant treatment before randomization

The medications (or classes of medications) listed in [Table 4.2.2.1: 1](#) must not be taken for the time periods as specified for washout.

Table 4.2.2.1: 1 Restricted medications

Medication or class of medications	Restriction duration
Biologic Treatments, e.g.: secukinumab (Cosentyx [®]), tildrakizumab (Ilumya [™]), rituximab, ustekinumab (Stelara [®]), risankizumab (Skyrizi [™]) natalizumab, alemtuzumab, guselkumab (Tremfya [®]), ixekizumab (Taltz [®]), adalimumab (Humira [®]), brodalumab, efalizumab, visilizumab, briakinumab. infliximab (Remicade [®]), certolizumab (Cimzia [®])	12 weeks or 5 half-lives, whichever is shorter, prior to Visit 2 (randomization)
Investigational products for psoriasis	12 weeks or 5 half-lives, whichever is shorter, prior to Visit 2 (randomization)
IL36R inhibitors	Not allowed
Etanercept (Enbrel [®]) live virus vaccinations ²	6 weeks prior to Visit 2
Any investigational device or product (excludes psoriasis products) Other systemic immunomodulating treatments (e.g. corticosteroids ¹ , cyclophosphamide), tofacitinib (Xeljanz [®]), apremilast (Otezla [®]) Other systemic psoriasis treatments (e.g. fumarates, any other drug known to possibly benefit psoriasis) photochemotherapy (e.g., PUVA).	4 weeks prior to Visit 2
GMA (Granulocytes and monocytes adsorptive apheresis) ²	4 weeks prior to Visit 2

(Contd. See next Page)

Table 4.2.2.1: 1 Restricted medications (cont'd)

Medication or class of medications	Restriction duration
Topical corticosteroids	Must be stopped at the day of randomization.
Anakinra (Kineret®)	7 days prior to Visit 2
methotrexate, cyclosporine, retinoids	Must be stopped at the day of randomization. Patients can be on these background medications at screening visit (V1), however they can only be randomized (V2) into this trial on the day of their next scheduled dose for the background treatment (where the patient should not take the dose) but instead be randomized on the trial.

¹No restriction on inhaled corticosteroids to treat asthma or corticosteroid drops administered in the eye or ear.

² Live virus vaccination and use of GMA should be restricted until the end of the trial.

In the event a patient with prior use of biologic treatment, systemic steroids or immunomodulating treatments is enrolled, past medical records are required to document when these treatments were stopped. All concomitant therapies will be recorded (including time of intake and dose on study days) on the appropriate pages of the CRF.

4.2.2.2 Restrictions regarding concomitant treatment during the trial (Post V2)

The following listed medications are not permitted throughout the study participation unless they are prescribed by investigators to treat disease worsening of GPP. However it is strongly recommended not to prescribe SoC even for GPP disease especially when patients are on the randomized treatment (See details about investigator-prescribed SoC for GPP disease in [Section 3.1](#) and [Section 4.2.1](#)). The use of Investigator Prescribed SoC for GPP will lead to the discontinuation of the trial treatment with some exceptions as described below.

Biologic Treatments:

Treatment with biologics are not allowed throughout the study.

Topical Treatments:

Topical treatment and any other therapies (e.g. Phototherapy) for GPP are not allowed throughout the study with the following exceptions:

- Topical treatment for other conditions (e.g. fungal infections, plaque psoriasis etc.) is allowed.
- Topical treatment is permitted for treatment of GPP after 4 weeks following i.v. dose rescue treatment with OL BI 655130 at R1/D1.
- Topical treatment is permitted for treatment of GPP during the OL maintenance treatment period.

Topical corticosteroids:

Topical corticosteroids for the treatment of GPP are not allowed throughout the study with the following exceptions:

- Topical corticosteroid for other conditions (e.g. fungal infections, plaque psoriasis etc.) may be initiated post visit 2 if needed.
- Topical corticosteroid is permitted for treatment of GPP after 4 weeks following i.v. dose rescue treatment with OL BI 655130 at R1/D1.
- Topical corticosteroid is permitted for treatment of GPP during the OL maintenance treatment period.

Systemic Immunomodulating Treatments:

Systemic immunomodulating treatments (e.g. corticosteroids, cyclophosphamide), tofacitinib (Xeljanz[®]), apremilast (Otezla[®]) and other systemic psoriasis treatments (e.g. fumarates, any other drug known to possibly benefit psoriasis) photochemotherapy (e.g., PUVA) for the treatment of GPP are not allowed.

Methotrexate, Cyclosporine, Retinoids:

- **Randomized Treatment Period:** Treatment with Methotrexate, Cyclosporine, Retinoids are not allowed.
- **Rescue Treatment Period and Open Label Maintenance Treatment Period:** Methotrexate, Cyclosporine, or Retinoids may be allowed for the treatment of GPP only for those who have received a flare rescue treatment with i.v. dose of BI 655130 and have a partial response to the rescue treatment as following.

After at least 4 weeks from the rescue treatment at R1/D1, it is recommended to first initiate treatment with topical corticosteroids to manage skin symptoms, and then if further adjunctive treatment is required, then methotrexate, cyclosporine and/or retinoids may be initiated and continued with stable dosing until the patient achieves GPPGA score 0 or 1 or as per the investigator's judgement.

Other Medications/Products:

Treatment with the following medications/products are not allowed throughout the study.

- Investigational products for psoriasis
- IL36R inhibitors
- Etanercept
- Live virus vaccinations
- Any investigational device or product (excludes psoriasis products)
- Anakinra (Kineret[®])
- GMA (Granulocytes and monocytes adsorptive apheresis)

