If a patient on randomized (blinded) treatments experiences disease worsening but does not meet the GPP flare definition (See [Table 3.1: 3](#)), it is highly recommended that the investigator does not prescribe Standard of Care (SoC) but to wait until the patient meets the definition of a GPP flare in order that an OL i.v. dose of BI 655130 may be administered instead at this time. During the randomized maintenance treatment period, if a patient is given any investigator prescribed SoC for GPP disease worsening, the patient needs to discontinue from any further study drug. Please refer to [section 3.3.4.1](#) for further details on handling of patients with premature treatment discontinuation.

Handling of Investigator Prescribed Standard of Care (SoC) for GPP disease during Rescue Treatment Period of the 1st GPP Flare:

Use of investigator prescribed SoC for GPP during the first 4 weeks of receiving i.v. rescue treatment with open label BI 655130 at R1/D1 is not allowed. The patient may be treated with SoC as per PI's discretion, but the patient needs to discontinue from any further study drug if SoC was given. In this case, the patient remains in the trial and, given his/her agreement, ideally should complete all the scheduled visits in rescue treatment period within [Flow Chart 2](#) and as per Table 3.1:1 and then the remaining study visits in [Flow Chart 1](#) as applicable up to Wk 48 from randomization. Please also refer to [section 3.3.4.1](#) for further details on handling of patients with premature treatment discontinuation.

If a patient achieves at least a partial response (See [Table 3.1: 1](#)) to i.v. rescue treatment with open label BI 655130, then topical treatments/topical corticosteroids, methotrexate, cyclosporine and retinoids may be used after four weeks following i.v. rescue treatment with open label BI 655130 at R1/D1. These patients may continue on receiving open label s.c. BI 655130.

See [section 4.2.2.2](#) for further details on the restricted medications list post visit 2 and exceptions.

Handling of Investigator Prescribed Standard of Care (SoC) for GPP disease during Open Label Maintenance Treatment Period:

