If the patient experiences any further disease worsening during the maintenance treatment with OL s.c. dose of 300 mg BI 655130 q12 weeks, investigator should treat the patient with intensified maintenance therapy with open label s.c. dose of 300 mg BI 655130 q4 weeks before prescribing any SoC. During the OL maintenance treatment period, if a patient is given any investigator prescribed SoC (with the exception of topical treatments/topical corticosteroids, methotrexate, cyclosporine and retinoids) for GPP disease worsening, the patient needs to discontinue from any further study drug. Please refer to [section 3.3.4.1](#) for further details on handling of patients with premature treatment discontinuation.

[figure not shown]
Table 3.1: 3 Study definitions

GPP Disease Worsening	Disease worsening is defined as worsening of clinical status or GPP skin and systemic symptoms requiring treatment intervention in the investigator's opinion. In the case that rescue medication with BI 655130 has not been given before, it is recommended, however, to wait until a patient meets the definition of a GPP flare in order that rescue medication could be administered instead of SoC.
GPP Flare	Increase in GPPGA score by ≥ 2 from baseline* and the pustular component of GPPGA ≥ 2 . *Baseline value for efficacy measurements is the last value measured before 1 st IMP dose at V2.
Rescue Medication (OL i.v. dose of BI 655130)	Rescue with open label (OL) i.v. dose of BI 655130 to treat the first GPP flare during randomized treatment period. Rescue medication with OL i.v. dose of BI 655130 is only allowed for the first flare during the 48 week randomized treatment period.
Criteria to receive rescue treatment with Open Label (OL) i.v. dose of 900 mg BI 655130 at R3/D8 of rescue treatment period	
 • For patients with GPPGA score of ≥ 3 and a pustular component of GPPGA of ≥ 2 at R1: the total GPPGA is ≥ 2 and the pustular component of GPPGA is ≥ 2 at R3/D8. • For patients with GPPGA score of 2 and a pustular component of GPPGA of ≥ 2 at R1: the pustular component of GPPGA is ≥ 2 at R3/D8
Response to GPP Flare Treatment	After rescue treatment with OL i.v. dose of BI 655130 (at R1/D1 or at R1/D1 and R3/D8), responders are patients who show no flare symptoms of moderate/severe intensity with a GPPGA score of <3 and a pustular component score of <2 . In addition, the patient must have a decrease in GPPGA score by ≥ 1 from R1/D1.

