Partial Response to GPP flare treatment	A GPPGA score 0 or 1 was not achieved, but a reduction in GPPGA score (to <3) or GPPGA pustule sub-score (to <2) was observed after receiving the rescue treatment with OL i.v. dose of BI 655130.
Criteria to switch the patient from OL s.c. dose of 300 mg BI 655130 q12 weeks to intensified maintenance therapy with open label s.c. dose of 300 mg BI 655130 q4 weeks	If patient's GPPGA total score increases by ≥ 1 (with or without the presence or new appearance of pustules), or if there is an increase in the pustular component of GPPGA ≥ 1 from any of the previous OL maintenance visit(s).

Table 3.1: 3 Study definitions (Contd.)

Investigator prescribed Standard of Care (SOC) for GPP Disease
	
• Medications used for treating worsening of GPP symptoms or clinical status (i.e. disease worsening) without GPP flare. It is recommended, however, to wait until a patient meets the definition of a GPP flare in order that rescue medication with BI 655130 could be administered instead in the case that rescue medication was never given before. 
Or
 
• Medications used for treating patients without a response of a GPP flare after two weeks following i.v. dose rescue treatment with open label BI 655130 at R1/D1 (see also Response of a GPP Flare above). 
Or
 
• Medications used for treating any new GPP flare (i.e. subsequent flares) after receiving rescue medication for the first GPP flare experienced by the patient on the trial. 
Note: Any use of Investigator Prescribed SoC for GPP disease during the trial will lead to the discontinuation of the trial treatment with the following exceptions. Use of topical treatment/topical corticosteroid, methotrexate, cyclosporine and retinoids is permitted after four weeks following i.v. dose rescue treatment with open label BI 655130 at R1/D1 and also during the OL maintenance treatment period. Refer to section 4.2.2.2 for further details.

--	---

Proprietary confidential information © 2022 Boehringer Ingelheim International GmbH or one or more of its affiliated companies

^{**} In an event a patient experiences 1st GPP flare, please refer to [Figure 3.1:2](#) and [Section 3.1](#) for further details.

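### Read literally, protocol Section 4.2.2.2 stops open-label drug in a rescued patient who cleared and later needs methotrexate, cyclosporine or a retinoid; Sections 3.1 and 4.2.1 do not

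*Protocol*

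**What the plan says.** The opening paragraph of protocol Section 4.2.2.2 sets a stop rule: "The use of Investigator Prescribed SoC for GPP will lead to the discontinuation of the trial treatment with some exceptions as described below".

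For methotrexate, cyclosporine and retinoids, one item in that section covers both the rescue period and open-label maintenance. It limits the exception to patients who were given i.v. BI 655130 for a flare "and have a partial response to the rescue treatment as following". From four weeks after rescue, and after topical corticosteroids have been tried, the drug may be started and "continued with stable dosing until the patient achieves GPPGA score 0 or 1". The sentence then allows the investigator's judgement as an alternative end point.

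Table 3.1:3 defines partial response: "A GPPGA score 0 or 1 was not achieved, but a reduction in GPPGA score" to below 3, or in the pustule subscore to below 2, was seen after rescue.

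The other places that deal with the same drugs are:

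- Section 3.1, rescue period: "If a patient achieves at least a partial response", these drugs may be used after four weeks and open-label s.c. dosing may continue. The reader is sent to Section 4.2.2.2 "for further details on the restricted medications list post visit 2 and exceptions".
- Section 3.1, open-label maintenance: standard of care for worsening ends study drug, "with the exception of topical treatments/topical corticosteroids, methotrexate, cyclosporine and retinoids". The investigator should intensify to q4w dosing first. No response condition is given.
- Table 3.1:3, Note on investigator-prescribed standard of care: the drugs are permitted from four weeks after rescue and during open-label maintenance, with no response condition. The entry it belongs to includes treatment of flares after the first.
- Section 4.2.1: the same exemption, again with no response condition.

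**The concern.** Whether study drug stops when methotrexate is prescribed is an operative dosing instruction. Section 4.2.2.2 ties the permission to a defined term that excludes patients at GPPGA 0 or 1. A patient who responded best to rescue would then lose open-label drug on starting one of these agents, while a patient with residual disease would keep it.

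Sites reading different sections would handle the same patient differently. Stopping also counts as premature discontinuation, and Section 3.1 offers the extension trial only to patients who completed treatment without it. SAP Section 7 tabulates open-label maintenance discontinuations by reason, so the inconsistency would show in those counts.

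Patients who clear are not an odd subgroup. Protocol Section 1.2 reports that all 7 patients in the open-label flare trial were clear or almost clear by week 4. That was a small trial of a single i.v. dose, so it gives no rate for this one.

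**Working it through.** The documents give no figure to reproduce, so the check sets the rules side by side and follows one patient through them.

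**Condition for staying on study drug while taking one of the three agents**

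| Place | Rescue period (after 4 weeks) | Open-label maintenance | Refers to |
|---|---|---|---|
| 4.2.2.2 | partial response only | partial response only | 3.1 and 4.2.1 |
| 3.1, rescue paragraph | partial response or better | not covered | 4.2.2.2 |
| 3.1, open-label maintenance paragraph | not covered | no response condition | no pointer to 4.2.2.2 |
| Table 3.1:3, Note | no response condition | no response condition | 4.2.2.2 |
| 4.2.1 | no response condition | no response condition | 4.2.2.2 and 3.1 |

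The references run in a circle. Section 4.2.2.2 itself says "See details about investigator-prescribed SoC for GPP disease in" Sections 3.1 and 4.2.1, and those sections point to 4.2.2.2. Nothing says which governs.

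**One patient.** Appendix 10.1.1 takes the mean of erythema, pustules and scaling; a mean above 0 and below 1.5 scores 1, and 2.5 to below 3.5 scores 3. Baseline GPPGA is 1.

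1. At rescue, subscores 3/3/3: (3+3+3)/3 = 3.00, GPPGA 3.
2. After rescue, 1/0/1: (1+0+1)/3 = 0.67, GPPGA 1. This is a response under Table 3.1:3 (GPPGA below 3, pustules below 2, fall of 2). It is not a partial response, because 0 or 1 was reached.
3. In open-label maintenance the patient worsens despite q4w intensification, to 3/2/3: (3+2+3)/3 = 2.67, GPPGA 3, pustules 2. The rise from baseline is 3 − 1 = 2 with pustules at 2, so this is a subsequent flare. Table 3.1:3 reserves i.v. rescue for the first flare.
4. Methotrexate is prescribed. Under Section 4.2.2.2 read literally, study drug stops. Under the maintenance paragraph of 3.1, the Table 3.1:3 Note and 4.2.1, it continues.

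**Which text is out of line.** Section 3.1 (handling of flares) starts open-label maintenance after response of the flare. Response requires GPPGA below 3, pustules below 2 and a fall of at least 1. A responder is therefore either at GPPGA 0 or 1, or at GPPGA 2 after falling from 3 or more, which is a partial response. If the condition in 4.2.2.2 is read as a minimum, every patient who entered maintenance as specified meets it, and 4.2.2.2 agrees with the other rules for that period. The conflict arises only because the text names the partial category alone.

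**A separate slip.** The rescue paragraph of 3.1 cites Table 3.1:1 for partial response. That table holds visit windows; the definition is in Table 3.1:3.

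**The case against.** The strongest reply is that the protocol has one sensible meaning. Three other places agree that study drug continues in open-label maintenance, Section 3.1 expresses the response condition as a minimum, and it makes no clinical sense to withdraw drug because a patient responded better. The Note in Table 3.1:3 covers subsequent flares directly, so the worked patient is provided for. Section 4.2.2.2 also lets the investigator keep a patient on the adjunct beyond GPPGA 0 or 1.

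Most of this stands, and it is why the point is treated as a drafting slip. It does not remove the inconsistency. Section 4.2.2.2 restricts the exception with the word only and uses a defined term, whereas 3.1 spells out a minimum when it means one. The investigator's-judgement clause governs how long an adjunct is continued, not who may start it.

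A reader might infer that a patient already on methotrexate must stop study drug on reaching GPPGA 0 or 1. That clause does not support this.

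A reader might also take response to mean status when the drug is prescribed. This is strained: Section 4.2.2.2 ties it to the rescue treatment, and Table 3.1:3 defines it by what was seen after rescue. The point does not depend on it.

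**Conclusion.** The inconsistency is real and minor. Section 4.2.2.2, taken with the Table 3.1:3 definition, excludes patients who cleared after rescue from an exception that Section 3.1, the Table 3.1:3 Note and Section 4.2.1 give them. The conclusion rests on the literal text; the likely intent is the wider rule.

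The number affected is unknown and probably very small. A patient must be rescued, clear, worsen again and then receive one of three drugs, and the documents give no rate for any later step. For maintenance, the group is further limited to patients rescued by Day 239. No patient count is offered here because none could be supported.

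A reader might infer that the efficacy results are at risk. They are not. Rescue use or a flare is already the event for the primary and key secondary endpoints (protocol Section 2.1; SAP Sections 5.1 and 5.2.1), so what follows in the open-label periods cannot change them, the alpha or the power. The effect is limited to open-label continuation, discontinuation counts and extension access.

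**What to change.** Make three wording changes:

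1. In Section 4.2.2.2, replace the partial-response condition with: at least a partial response to the rescue treatment (including patients who reached GPPGA 0 or 1).
2. In the open-label maintenance paragraph of Section 3.1, add a reference to Section 4.2.2.2.
3. In the rescue-period paragraph of Section 3.1, change the pointer for partial response from Table 3.1:1 to Table 3.1:3.

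The cost is protocol wording and a short memo to sites. No visits, assessments or analyses change.
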